4.1 Full Analysis Sets

The Full analysis set is defined as all subjects who received at least 1 dose of study treatment. All efficacy and safety analyses will use the full analysis set except for the endpoints of DOR and TTR, which will be conducted on the subjects in the full analysis set with an objective response (CR or partial response [PR]).

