8 EFFICACY ANALYSES

For the primary efficacy analysis, all response assessment data will be included regardless of how many Restriction Switches the subjects had.

Efficacy analyses will be conducted by cohorts and combined cohorts, as specified in Section 4.2.

Disease assessments performed by investigators regardless of modalities will be grouped into one timepoint assessment if the gap between two consecutive disease assessments is less than or equal to 14 days. This grouping will continue for the same timepoint assessment until the gap between two consecutive disease assessments exceeds 14 days.

The ranking for assessment modalities is specified in Table 2. If there are multiple assessments with the same modality in the same timepoint assessment, the worst/worse assessment (from the best to the worst in the order of not evaluable [NE], CR, PR, stable disease [SD] and progressive disease [PD]) will be selected for that modality. If there are assessments based on multiple modalities for a timepoint assessment, then the overall response for the timepoint assessment will be decided by the rank of the modalities specified in Table 2. For example, for a timepoint assessment, a PR was assessed per biopsy and a CR was assessed per physical examination. The assessment per biopsy will override that of physical examination for this timepoint assessment. If PD is determined as the response for a timepoint assessment, the earliest assessment date among all the disease assessments for this timepoint assessment will be considered as the PD date. If SD, PR or CR is determined as the response for a time assessment, the latest assessment date among all the disease assessments for this timepoint assessment will be considered as the response date.

While in general if any therapy directed towards the disease being treated, other than protocol-specified treatment, is initiated, response data after the initiation date of such therapy may be censored. However, given the fact that some anti-underlying disease therapies were actually allowed per the protocol, in the primary analysis of disease assessment related endpoints, none of such therapies were considered for censoring rule. As a sensitivity analysis, response data after the initiation of such therapies are censored, and such analysis is conducted for the endpoints including ORR, DOR, and PFS based on the Full Analysis Set.

Table 2: Rank of the Modalities (1 indicates highest rank)

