8.1 Analysis of Primary Endpoints

The primary endpoint ORR and its corresponding 95% CI will be reported by cohorts and combined cohorts specified in Section 4.3. The primary endpoint ORR is the proportion of subjects who have achieved a CR or PR during the study.

Sensitivity analysis will be conducted for ORR excluding response data after the initiation of any non-protocol anti-underlying disease therapies.

CCI
[REDACTED]

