8.2.2 Duration of Response

Duration of response is calculated based on subjects who achieve CR or PR. DOR is defined as the time from the date of initial response until (1) progression after the last response or (2) death due to any cause.

Only deaths within 90 days after the last valid disease evaluation (ie, not NE) will be counted as events in the DOR definition above.

For subjects without an event of death or disease progression, DOR is censored at the last valid (not NE) disease evaluation date.

In a sensitivity analysis, if any anti-underlying disease therapy is initialized before the event date/censoring date, DOR is censored at the last assessment date prior to the therapy initialization.

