8.2.3 Progression-free Survival

Progression-free survival is defined as the time from the first dose of study treatment to either of following events whichever occurs first: (1) progression after the last response or (2) death due to any cause.

Death within 90 days after last valid disease evaluation (ie, not NE), or first study treatment dose date if there is no valid post-baseline disease evaluation, will be counted as events in the PFS definition

For subjects without an event as defined above, PFS will be censored at

- Last valid (not NE) post -baseline disease evaluation date
- First dose date if there is no valid post-baseline disease evaluation.

As a sensitivity analysis, PFS will be defined as the time from the first dose of tabelecleucel to either of following events, whichever occurs first, (1) the first progression or (2) death due to any cause. All other details and censoring rules are the same as above for the primary PFS analysis.

In another sensitivity analysis, if any anti-underlying disease therapy is initialized before the event date/censoring date, PFS is censored at the last assessment date prior to the therapy initialization.

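### For subjects who respond after starting a new anti-disease therapy, the therapy-censoring rule for DOR and PFS, read literally, can recode a documented progression as censored and conflicts with SAP section 8

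*SAP*

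**What the plan says.** SAP 8.2.2 defines DOR as "the time from the date of initial response until (1) progression after the last response or (2) death due to any cause". SAP 8.2.3 defines PFS from first dose to "either of following events whichever occurs first: (1) progression after the last response or (2) death due to any cause". In both, a later response cancels an earlier progression as the event.

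SAP section 8 states that in the main analysis "none of such therapies were considered for censoring rule". A response seen after a new therapy therefore counts in full.

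The sensitivity handling appears in two forms.

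- **General form.** SAP 8, naming ORR, DOR and PFS: "As a sensitivity analysis, response data after the initiation of such therapies are censored". SAP 8.1 repeats it for ORR: "Sensitivity analysis will be conducted for ORR excluding response data after the initiation of any non-protocol anti-underlying disease therapies".
- **Endpoint form.** SAP 8.2.2: "if any anti-underlying disease therapy is initialized before the event date/censoring date, DOR is censored at the last assessment date prior to the therapy initialization". SAP 8.2.3: "PFS is censored at the last assessment date prior to the therapy initialization", with the same trigger.

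The DOR population is given once. SAP 4.1 makes DOR an exception to the full analysis set, "which will be conducted on the subjects in the full analysis set with an objective response" (CR or PR). No separate responder set is named for the sensitivity analysis. SAP 8.2.3 also plans a second PFS sensitivity analysis that takes the first progression as the event; SAP 8.2.2 has no counterpart for DOR.

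**The concern.** The endpoint rule compares the therapy date with an event or censoring date that the therapy itself can postpone. If the subject responds after the new therapy, the final response is now post-therapy and the event date lies later still. The trigger is met, and follow-up is cut at the last assessment before therapy. Where that assessment was the progression that led to the new therapy, the progression becomes a censored observation on its own date. The rule states no exception for this.

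The sequence is foreseeable. Protocol section VIII (Post-Infusion Evaluation) allows alternative therapy at progression. SAP 4.2 classes transplant donor-derived or autologous EBV-CTLs given after tabelecleucel as other anti-disease therapy and allows censoring for it in sensitivity analysis.

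At stake is the purpose of the analysis. It is the only planned DOR check on the influence of other therapy. For these subjects the main DOR runs through the first progression and the sensitivity DOR censors it, so that progression is an event in neither. SAP 11 plans no formal test on CR and relies on estimates, including DOR, shown by cohort. In a small cohort a few recoded subjects could be visible.

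**Working it through.** The plan states no figure here, so the check applies the rules to illustrative records. All days are assumptions, counted from first dose. Consecutive assessments are more than 14 days apart, so the SAP's grouping of assessments into timepoints plays no part. For a subject who never responds, the first progression is taken as the event.

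**Rules applied**

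- Main: end = first progression after the final CR or PR, otherwise last assessment. DOR = end − first response; PFS = end.
- As written (8.2.2, 8.2.3): if therapy day < main end, censor at the last assessment before therapy.
- Cut first (8, 8.1): drop assessments after therapy start, then apply the main rule.

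| Record | Main | As written | Cut first |
|---|---|---|---|
| A: PR 30, PD 100, therapy 110, no later response | PFS 100 event; DOR 70 | PFS 100 event; DOR 70 | PFS 100 event; DOR 70 |
| B: PR 30, PD 100, therapy 110, CR 150, PD 300 | PFS 300 event; DOR 270 | PFS 100 **censored**; DOR 70 **censored** | PFS 100 **event**; DOR 70 **event** |
| C: as B, no second PD to day 400 | PFS 400 censored; DOR 370 | PFS 100 **censored**; DOR 70 **censored** | PFS 100 **event**; DOR 70 **event** |
| D: PD 40, therapy 50, CR 90, PD 300 | PFS 300 event; DOR 210 | PFS 40 **censored**; DOR 40 − 90 = **−50** | PFS 40 **event**; not in DOR set |
| E: SD 40, therapy 50, CR 90, no PD to day 300 | PFS 300 censored; DOR 210 | PFS 40 censored; DOR 40 − 90 = **−50** | PFS 40 censored; not in DOR set |
| F: PR 30, PR 55, therapy 60, PD 100 | PFS 100 event; DOR 70 | PFS 55 censored; DOR 25 | PFS 55 censored; DOR 25 |
| G: PD 40, therapy 50, never responds | PFS 40 event | PFS 40 event | PFS 40 event |

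A and G, where progression precedes therapy and no response follows, are handled properly: therapy on day 110 or 50 is after the event on day 100 or 40, so the rule does not fire. F, where therapy starts during response, is also as intended. The two forms of the rule part only in B to E, where a response follows the therapy.

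**Illustration of size.** Assume 20 responders, 6 progressing between days 30 and 180 of response, and 14 followed beyond that. With all 6 as events, the 6-month Kaplan-Meier DOR is 14/20 = 0.700. Recoding one progression as censored on its own date removes its factor (n − 1)/n, where n is the number at risk, from 20 down to 15. The estimate becomes 0.700 × n/(n − 1), between 0.700 × 20/19 = 0.737 and 0.700 × 15/14 = 0.750, averaging 0.743. The same averaging for 2, 3 and 4 recoded subjects gives 0.788, 0.837 and 0.888.

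**The case against.** The best defence is that SAP 8 already governs. It names DOR and PFS and discards response data after the new therapy. If that is done first, the later response does not exist, the earlier progression is the event, the trigger is not met, and a subject whose only response came after therapy is not a responder. On that view the endpoint sections merely abbreviate the general rule.

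Part of this stands. SAP 8 and 8.1 show what was probably intended, and they point against keeping post-therapy responders in the DOR set. It does not settle the matter. If post-therapy assessments were removed first, the event or censoring date could hardly ever fall after the therapy, deaths aside, and the trigger in 8.2.2 and 8.2.3 would have almost nothing to act on. The natural reading of that trigger uses the main-analysis date, and a programmer would be likely to code the endpoint-specific text.

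A reader might infer two stronger things.

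- That the rule censors progressions generally whenever new therapy follows them. It does not; records A and G keep theirs.
- That both DOR and PFS are overstated in every planned analysis. For PFS this fails, because the first-progression sensitivity analysis keeps the earlier progression.

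It is also fair to object that the Kaplan-Meier counts are invented. The values for 3 or 4 recoded subjects need half to two-thirds of progressors to respond after a new therapy, and nothing in the documents supports such a rate.

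**Conclusion.** The point holds for a defined subset: subjects who respond after starting a new anti-disease therapy. For them SAP 8.2.2 and 8.2.3, read literally, give a different answer from SAP 8 and 8.1. A progression documented at the last pre-therapy assessment turns from event to censored. A negative DOR follows only if the first response came after the therapy and the subject is kept in the responder set, which the SAP neither states nor rules out in 8.2.2. DOR is the more exposed endpoint, since it has no second sensitivity analysis.

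The size cannot be given, because the number of such subjects is not in the documents. Under the assumed 20 responders and 6 progressions, one recoded subject moves the 6-month estimate from 0.70 to about 0.74 and two move it to about 0.79. These are descriptive sensitivity analyses of secondary endpoints, so the primary ORR result is untouched. The clarification is worth making because it is cheap and the rule as written can weaken the check it is meant to provide.

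**What to change.** State the order of operations in SAP 8.2.2 and 8.2.3, for example:

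*In this sensitivity analysis, for subjects who start an anti-underlying-disease therapy after first dose (including EBV-CTL products classed as such therapy in Section 4.2), response, the DOR responder set and progression are re-derived using only assessments dated on or before the therapy start, before assessments are grouped into timepoints. A progression on or before the therapy start that follows the last such response, or any such progression if there was no response, is an event. Otherwise the subject is censored at the last valid (not NE) post-baseline assessment on or before the therapy start, or for PFS at the first dose date if there is none. Death rules for subjects with no new therapy are unchanged.*

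Using on or before, rather than before, keeps a progression scan dated on the day the therapy starts. Naming the switched EBV-CTL products avoids dropping them from the rule because they are study products. Restricting the DOR set to responses on or before the therapy start makes a negative duration impossible.

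The cost is a wording change and minor reprogramming on data already held. Sensitivity DOR and PFS may look slightly less favourable.

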8.2.3 Progression-free Survival

Progression-free survival is defined as the time from the first dose of study treatment to either of following events whichever occurs first: (1) progression after the last response or (2) death due to any cause.

Death within 90 days after last valid disease evaluation (ie, not NE), or first study treatment dose date if there is no valid post-baseline disease evaluation, will be counted as events in the PFS definition

For subjects without an event as defined above, PFS will be censored at

- Last valid (not NE) post -baseline disease evaluation date
- First dose date if there is no valid post-baseline disease evaluation.

As a sensitivity analysis, PFS will be defined as the time from the first dose of tabelecleucel to either of following events, whichever occurs first, (1) the first progression or (2) death due to any cause. All other details and censoring rules are the same as above for the primary PFS analysis.

In another sensitivity analysis, if any anti-underlying disease therapy is initialized before the event date/censoring date, PFS is censored at the last assessment date prior to the therapy initialization.

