Other EBV+ Disorders with ID	HCT/SOT EBV+ PTLD	EBV+ Malignancy without ID
		EBV-CTL Tab-cel
		(Transplant donor derived) NPC Total (cohort 32) (cohort 107+32)
	Total	Lymphoma
AID LPD PID LPD Viremia LMS (cohort 5, (cohort 1,2,101,102, (Cohort 107)	(cohort 6+106, (cohort 106, 101, 102, 103)	Total (all cohorts)
(cohort 5) 6+106) 171) 31) 171, 31) 4, 103) 107)		

Table d: *Other cohorts and All cohorts – tabelecleucel only*:

Other EBV+ Disorders with ID	HCT/SOT EBV+ PTLD	EBV+ Malignancy without ID
		Tab-cel Total
AID PID LMS (cohort 1,2, (cohort 101,102, (Cohort 1+2) (Cohort 4) (cohort 1,2,4) Tab-cel Total (cohort 5) LPD LPD (cohort 31) 4, 103) (Cohort 103) (Cohort 4) 32) (all cohorts)	HCT EBV+ SOT EBV+ Total NPC (cohort 32) (cohort 1,2,4) 32) tab-cel	

Efficacy will be summarized as in the following headers:

Table a: HCT Cohorts:

Tab-cel HCT EBV ⁺ PTLD				EBV-CTL (Transplant donor derived)			
R/R	Rituximab	R/R	Rituximab	EBV ⁺ PTLD	Total	(cohort	Total
Rituximab	Naïve	Total	Rituximab	Naïve	(cohort	(cohort 1)	(cohort 102)
(cohort 1)	(cohort 2)	(cohort 1+2)	(cohort 101)	(cohort 102)	101+102)		

Table b: *SOT Cohorts:*

Tab-cel SOT EBV ⁺ PTLD R/R	EBV-CTL (Transplant donor derived) SOT EBV ⁺ PTLD
Rituximab+Chemo (cohort 4)	(cohort 103)

Table c: *Other cohorts and All cohorts:*

Other EBV ⁺ Disorders with ID				EBV ⁺ Malignancy without ID		
AID	PID	Viremia	LMS	EBV-CTL (Transplant donor derived)	Lymphoma	Tab-cel NPC
LPD (cohort 5)	(cohort 6+106)	(cohort 171)	(cohort 31)	(Cohort 107)		(cohort 32)

Table d: *Other cohorts and All cohorts – tabelecleucel only:*

Other EBV ⁺ Disorders with ID				EBV ⁺ Malignancy without ID
AID (cohort 5)	PID (cohort 6)	Viremia (cohort 31)	LMS (cohort 31)	Tab-cel NPC (cohort 32)

Cohort Assignment for Subjects with > 1 Source of Study Treatment

Some subjects may receive EBV-CTLs from > 1 donor source type (Section 2.4) during the study. As a general rule for efficacy analysis, any transplant donor-derived or autologous EBV-CTL treatment received after the initiation of tabelecleucel will be considered as other anti-underlying EBV⁺ disease therapy. For such subjects, the efficacy analysis may be censored due to the initiation of this therapy in sensitivity analysis.

The efficacy and safety data for a subject who starts with tabelecleucel and then switches to either transplant donor-derived or autologous EBV-CTLs will be presented under the relevant tabelecleucel cohort.

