Each subject who first receives an EBV-CTL product other than tabelecleucel and then switches to a different non-tabelecleucel EBV-CTL product (eg, transplant donor-derived followed by autologous) will be considered as 2 independent subjects for the purposes of analysis. The efficacy and safety data for such a subject will be assigned to the relevant study treatment source cohort based on the initial dose of each product type.

A subject who first receives an EBV-CTL product other than tabelecleucel, switches to tabelecleucel, and then switches to a non-tabelecleucel EBV-CTL product, will be considered as 2 independent subjects, based on the first 2 study treatments received, for the purposes of analysis. The efficacy and safety data for such a subject will be assigned to the relevant study treatment source cohort based on the initial dose of the first 2 product types. The third EBV-CTL product will be considered as other anti- post-transplant lymphoproliferative disorder (PTLD) therapy.

Data for subjects assigned to the autologous EBV-CTL cohort will not be included in the summary tables or figures. The efficacy and safety data for these subjects during autologous EBV-CTL treatment will be provided in the listings.

Regardless of the number of products received, all subjects will be counted only once in the ‘Overall Total’ combined cohort for safety analyses.

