8.2.5 Time to Progression

Time to progression (TTP) is defined as the time from the date of the first dose of study treatment to progression after the last response. Death within 90 days after the last valid post-baseline disease evaluation, or after first dose date if there is no valid post-baseline disease evaluation, will be counted as an event only if the death reason is due to disease progression. Data will be censored on the death date if such deaths are not due to disease progression. The other censoring rules are the same as the ones used for the primary analysis of PFS in Section 8.2.3.

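### As written, primary PFS and TTP give no progression event to a subject who never reaches CR or PR, although both are analysed on the Full Analysis Set.

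*SAP*

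**What the plan says.** **Event definitions.** Primary PFS (SAP 8.2.3) runs from the first dose of study treatment to "whichever occurs first: (1) progression after the last response or (2) death due to any cause". TTP (SAP 8.2.5) is "the time from the date of the first dose of study treatment to progression after the last response". DOR (SAP 8.2.2) ends at the same kind of progression, or at death. DRR (SAP 8.2.4) requires a response lasting more than six months and has no progression rule of its own.

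**Population.** SAP 4.1: "All efficacy and safety analyses will use the full analysis set except for the endpoints of DOR and TTR". Only DOR and TTR are restricted to subjects with CR or PR, so PFS and TTP include everyone treated.

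**Censoring.** A subject without a PFS event is censored at the last valid post-baseline evaluation, or at first dose if there is none. A death within 90 days of that date counts for PFS. For TTP it counts only if due to disease progression. TTP takes its other censoring rules from primary PFS.

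**Sensitivity analyses.** SAP 8.2.3 adds a PFS analysis that counts the first progression, but times it from the first dose of tabelecleucel. TTP, DOR and DRR have no first-progression version. After a change of tabelecleucel line for lack of efficacy (a Restriction Switch), SAP 8 states that "all response assessment data will be included regardless of how many Restriction Switches the subjects had".

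**The concern.** Tying the event to the last response suits DOR, where every subject has responded. Carried into PFS and TTP, it leaves out the never-responders, the subjects most likely to progress early. If their progression is not an event and they leave the risk set at the progression visit, the censoring depends directly on the outcome. Kaplan-Meier then treats them as if their prospects matched those of the subjects still at risk, who are mostly responders.

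Two programmers could follow these sections faithfully and produce different PFS and TTP curves.

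A related gap affects responders. A progression followed by a new response is ignored in PFS, TTP, DOR and, by inference, DRR. Carrying a duration through a Restriction Switch is a defensible choice. However, only PFS has a first-progression result to set beside it, so for the other three endpoints the reader cannot see directly what that choice contributes.

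**Working it through.** The documents state no PFS, TTP, DOR or DRR figure to reproduce. The check applies the text to each type of subject and then sizes the effect under assumed rates.

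**1. What response means.** SAP 4.1, 8.1 and 8.2.6 tie it to CR or PR. SAP 8 also uses the word for any timepoint category: "If SD, PR or CR is determined as the response for a time assessment" and "If PD is determined as the response for a timepoint assessment". Neither wider sense gives a workable rule. If SD counts as a response, a subject whose first evaluation is PD still has no event. If PD also counts, progression after the last response has no clear meaning.

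**2. Literal outcome by type of subject.**

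| Subject | Primary PFS | TTP |
|---|---|---|
| Never CR/PR, PD, no death within 90 days of last valid evaluation | Censored at that evaluation | Censored at that evaluation |
| Never CR/PR, PD, death within 90 days | Event dated at death, not at PD | Event only if death is due to progression; otherwise censored at death |
| Response, PD, later response | First PD ignored | First PD ignored |

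**3. Size, simple case (all rates assumed).** Let r be the proportion responding, all event-free to month 6. Never-responders have PD at day 35 as their last valid evaluation. Day 35 follows from the protocol schedule: third infusion on day 14 plus three weeks. A share d of them die within 90 days of PD, hence by day 125.

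- First-progression rule: six-month PFS = r.
- Literal rule: (1−r)(1−d) are censored at day 35, leaving r + (1−r)d at risk. Of these, (1−r)d die before month 6, so six-month PFS = r / [r + (1−r)d].

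With r = 0.5:

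| d | Literal | First progression |
|---|---|---|
| 0 | 0.5/0.5 = 100% | 50% |
| 0.5 | 0.5/0.75 = 66.7% | 50% |
| 0.9 | 0.5/0.95 = 52.6% | 50% |
| 1 | 0.5/1 = 50% | 50% (literal events fall later, at death) |

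TTP gives the same figures if every such death is due to progression. Deaths from other causes become censorings, so the gap is then no smaller. Evaluations continued after PD would delay the censoring without restoring the event.

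**4. Size, wider case (all rates assumed).** Simulation of 400,000 subjects, assessed on days 35, 70, 91, 122, 152 and 183. Half of the never-responders progress at day 35 and half at day 70. Entries are six-month PFS.

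| r | d | Responders progression-free at month 6 | Literal | Response = SD, PR or CR | First progression |
|---|---|---|---|---|---|
| 0.4 | 0.3 | 100% | 0.703 | 0.507 | 0.400 |
| 0.5 | 0.5 | 80% | 0.543 | 0.457 | 0.400 |
| 0.7 | 0.7 | 60% | 0.466 | 0.441 | 0.421 |

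With r from 0.4 to 0.7, d from 0.3 to 0.7 and 60–100% of responders progression-free at month 6, the excess is about 5 to 30 points on the literal reading and 2 to 11 if SD counts as a response. With d = 0.9 it is 1.4 to 2.9 and 0.6 to 1.3 points. It is zero if first progression counts for all never-responders.

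**5. Progression then a new response (invented subject, days from first dose).** PR day 35, PD day 70, CR day 140 after a Restriction Switch, PD day 300. DOR is 300 − 35 = 265 days, which is durable because six months is 6 × 365.25/12 = 182.6 days. By first progression it is 70 − 35 = 35 days. PFS is 300 days against 70. The documents do not say how often this happens. Donor-derived or autologous cells given later are handled differently: "any transplant donor-derived or autologous EBV-CTL treatment received after the initiation of tabelecleucel will be considered as other" disease therapy. The censoring sensitivity analyses for DOR and PFS therefore cover those cells, but not a Restriction Switch.

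**6. Time origin.** The first-progression PFS analysis, OS, TTR and clinical benefit rate all start at the first tabelecleucel dose. Subjects given only transplant donor-derived cells (cohorts 101, 102, 103, 106, 107 and 171 in SAP Table 1) have no such dose.

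**The case against.** The best defence is intent. SAP 8.2.3 and 8.2.5 count certain deaths in subjects with no valid post-baseline evaluation, who cannot have responded. It would be incoherent to count those and deliberately ignore documented progression in a non-responder. The natural reading is that a PD is set aside only when a response follows it. That argument stands as evidence of intent. It supplies no rule for documented PD, and because SAP 8.2.3 says first progression in its sensitivity analysis and uses other words in the primary one, a programmer could take the contrast as deliberate.

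The existing first-progression PFS analysis is also a fair point: it shows the effect on PFS in the tabelecleucel cohorts and informs TTP indirectly. It does not repair the primary definition or TTP, and its starting date is undefined for donor-derived-only subjects. The intended date can probably be recovered, since SAP 4.2 assigns subjects who switch products to cohorts "based on the initial dose of each product type".

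Three stronger readings go beyond the documents:

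- **That first progression should replace the primary definition for everyone.** The SAP openly keeps data after a Restriction Switch, and that choice is legitimate for responders.
- **That PFS excludes all deaths later than 90 days.** The restriction is explicit for DOR. For PFS it is only implied, because the definition also lists death from any cause. The effect would depend on visit timing, which the protocol calls approximate.
- **That PFS is known to be inflated by a stated amount.** Every rate above is assumed, and the bias disappears on the probable intended reading.

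**Conclusion.** The point holds as a defect in the written definitions of primary PFS and TTP: a never-responder's documented progression is not an event, and no section supplies the missing rule. If the text is programmed literally, both endpoints are likely to read too high. The illustrative size is 67% against 50% at six months, assuming that half respond and stay event-free, that the rest progress at day 35 with no later evaluation, and that half of those die within 90 days. The excess shrinks to 2–3 points if 90% die in that window, and to zero if first progression is counted.

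It should be fixed, but the stakes are bounded. PFS and TTP are secondary and descriptive, SAP 11 plans no formal test on CR, and primary ORR is unaffected. OS is affected only by the time-origin wording. DOR and DRR do not have the never-responder gap, because both require a response. For them the issue is only the missing first-progression comparison.

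**What to change.** 1. In SAP 8.2.3 and 8.2.5, state that for subjects without CR or PR the event is the first PD after first dose. Keep progression after the last response for responders.
2. Add first-progression sensitivity versions of TTP, DOR and DRR, to match the one PFS already has.
3. Time the first-progression PFS analysis, OS, TTR and clinical benefit rate from the first dose of the study treatment that defines the cohort. This also fits subjects counted in two cohorts.
4. Optional: say whether the 90-day limit on deaths applies to PFS as it does to DOR, and add an analysis counting all deaths.

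The cost is a few sentences of SAP text, some re-derivation from data already collected and a little extra output. The secondary figures may look less favourable.
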